137 which we are aware, the adaptive basal insulin algorithm obviates the need for the user to set, or even know, his
138 or her "basal-rate profile". Instead, it is capable of automatically adapting to, and compensating for, changes in
139 an individual's basal insulin need, such as might occur over a period of hours, days, or weeks (e.g. circadian
140 hormonal fluctuations, intercurrent illness, physical activity, or emotional state) or as might occur over a period
141 of months or years due to developmental changes (e.g. hormonal changes that occur during puberty or
142 menopause). Our adaptive meal dose controller obviates the need for the user to set, or even know, his or her
143 "carbohydrate-to-insulin ratios", as it makes automatic adjustments based on dosing history for similar meal
144 announcements made on previous days, and customizes the dose for each individual and for time of day. Our
145 BP also includes a proportional-derivative algorithm governing SC micro-doses of glucagon to help prevent
146 impending hypoglycemia. Glucagon dosing is based on the glucose level and rate of descent. It could occur
147 preemptively even if glucose is above range and it includes a feedback term to account for the pending effects
148 of recent glucagon doses.

149
150 Taken together, these mathematical algorithms provide a universal framework for a glycemic control strategy
151 that requires no quantitative input from, or participation by, the user (besides entering body weight to initialize
152 the system), but which automatically adapts insulin and glucagon dosing to meet the individual needs of each
153 user. Another challenge we have met is enabling the technology to remain completely autonomous in managing
154 insulin and glucagon delivery even when the Dexcom CGM is offline. Specifically, when the Dexcom CGM is
155 offline, the BP invokes the high-resolution "basal rate profile" that it had recently learned and stored when the
156 Dexcom CGM was online. On the basis of what the system learned and stored about meal announcements when
157 the Dexcom CGM was online, it is able to respond to meal announcements in the same manner when the Dexcom
158 CGM is offline. Finally, it automatically responds to user-entered BG values when the Dexcom CGM is offline by
159 issuing a correction dose of insulin or glucagon based on what it learned about the user's insulin and glucagon

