235 pancreas in preventing hypoglycemia during mild exercise of extended duration in the fasted state.
236

237 Twenty subjects will participate in two experimental periods. Each will include a 24-96 hour outpatient run-in
238 period prior to their exercise visit wearing the bi-hormonal bionic pancreas. This will allow the bionic pancreas
239 to adapt to their diabetes management needs. After the run-in period is complete, the subjects will participate
240 in an exercise visit during which they will arrive fasting and remain fasted until the visit is completed. Subjects
241 will walk on a treadmill for up to 1 hour at a comfortable walking pace. Plasma glucose (PG) measurements will
242 be performed frequently. In one experimental period the bionic pancreas will remain in the bihormonal
243 configuration and will deliver glucagon as needed during the exercise visit. In the other experimental period the
244 glucagon will be replaced with a placebo during the exercise visit. The two experimental periods will be
245 performed in random order. The study will be performed in single-blind fashion in that the participant will not
246 know whether the bionic pancreas glucagon pump is filled with glucagon or placebo during the exercise visits.
247 The outpatient run-in period will always be with the bi-hormonal bionic pancreas delivering glucagon.
248

249 **Aim 2.** To collect samples of breath and sweat during hypoglycemia in 20 adult (≥ 18 years of age) subjects with
250 type 1 diabetes.
251

252 Breath and sweat samples will be collected at intervals throughout the exercise visits, with increased frequency
253 during hypoglycemia. Collaborators with the MITRE Corporation will perform analyses on these samples to
254 identify any relationships between volatile organic compounds in breath and sweat and hypoglycemia.
255

256 **III. Subject Selection**

257 **III. a. Inclusion Criteria**

- 259 • Informed consent by the subject documented prior to any study procedures
- 260 • Age ≥ 18 years and have had clinical type 1 diabetes for at least one year
- 261 • Diabetes managed using an insulin pump for ≥ 6 months
- 262 • Have used a CGM for ≥ 4 weeks over the last 12 months (usage does not need to be consecutive)
- 263 • Prescription medication regimen stable for > 1 month (except for medications that will not affect the
264 safety of the study and are not expected to affect any outcome of the study, in the judgment of the
265 principal investigator)

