- 944 • Time from the start of exercise to first PG < 60 mg/dl, if found

945

946 **VI. b. 3. Other endpoint analyses**

947

948 **Exercise and post-exercise monitoring period**

- 949 • Plasma glucose at the start of exercise
- 950 • Mean slope of the CGM glucose curve in the 30 minutes prior to the start of exercise
- 951 • Area over the plasma glucose curve and <60 mg/dl accumulated at the time the participant requests
- 952 carbohydrate treatment or treatment is required by protocol during exercise visit
- 953 • Duration with CGM glucose <60 mg/dl during exercise visit
- 954 • Nadir CGM glucose during exercise visit
- 955 • Area over the plasma glucose curve and <60 mg/dl during exercise visit, calculated by CGM
- 956 • Time from the start of exercise to first CGM reading < 60 mg/dl

- 957 • Total glucagon dosing by bi-hormonal bionic pancreas from the start of exercise until the end of the
958 exercise and post-exercise monitoring period
- 959 • Grams of oral carbohydrates given to the subject to treat hypoglycemia during the exercise and post-
960 exercise monitoring period
- 961 • Total glucagon dosing by bi-hormonal bionic pancreas from the start of exercise until the end of the visit
- 962 • **VOC outcomes**
- 963 • Identification of volatile and organic compound or compounds in breath and sweat that correlate(s)
964 with hypoglycemia
- 965 • Identification of volatile organic compounds in breath and sweat that correlate with normoglycemia
966 and/or hyperglycemia
- 967
- 968

969 **Outpatient period**

- 970 • **CGM-based outcomes**
- 971 • Mean CGM glucose – 24-hours, daytime (7:00 AM – 11:00 PM), and nighttime (11:00 PM – 7:00 AM)
- 972 • Time in the following ranges – 24-hours, daytime (7:00 AM – 11:00 PM), and nighttime (11:00 PM –
973 7:00 AM):
- 974 ○ <70 mg/dl
- 975 ○ <60 mg/dl
- 976 ○ <54 mg/dl
- 977 ○ <50 mg/dl
- 978 ○ 70-180 mg/dl
- 979 ○ 70-120 mg/dl
- 980 ○ 70-140 mg/dl
- 981 ○ >180 mg/dl
- 982 ○ >250 mg/dl
- 983 • Percentage of participants achieving a mean CGM glucose of ≤ 154 mg/dl
- 984 • Correlation between mean Dexcom CGMG and mean number of meal announcements per day
- 985 • CGM MARD from Dexcom G5 CGM versus time-stamped BG values from meter downloads (any other
986 BG values will not be considered)
- 987 • CGM Reliability index, calculated as percent of possible values actually recorded by CGM
- 988 • **PG-based outcomes**

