1019 from periods when the bionic pancreas was not in use, if available (Dexcom CGM data may not be available in
1020 some failure modes). In cases where an arm was not completed we will use the available data from that arm in
1021 the data analysis. We will calculate percentages, means standard deviations (and medians and interquartile
1022 ranges as appropriate), and ranges in descriptive analyses. We will use the Shapiro-Wilk test to determine
1023 normality of the variables. We will use paired t-test for comparison of means for normally distributed
1024 outcomes and the Wilcoxon Signed Rank test for comparisons on non-normally distributed outcomes. In a
1025 secondary analysis we will look for any period effect in normally distributed outcomes and any interaction
1026 between treatment and period, although no such interaction is predicted and there is probably insufficient
1027 power to identify a small interaction. We may, in exploratory analyses, also stratify subjects for secondary
1028 analyses of the pre-specified endpoints by the following characteristics: sex, age, usual care insulin total daily
1029 dose, body mass index, baseline A1c, and use of CGM in usual care.

1030
1031 **VI. c. Power Analysis**

1032 **Power Calculation for Aim 1**

1033 The sample size for this study is being based on the power calculations for Aim 1. From our clinical experience,
1034 we expect the hypoglycemia rate to be around 25% in the bi-hormonal arm and around 75% in the insulin-only
1035 arm, corresponding to a difference of 50 percentage points.

1036 The table below provides power calculations of a two-sided exact McNemar's test with 2.5% type I error under
1037 varying degrees of within-subject correlations.

1038 Based on our clinical experience with bi-hormonal bionic pancreas, patients who develop hypoglycemia using bi-
1039 hormonal bionic pancreas are highly likely to also develop hypoglycemia when not given glucagon. We expect
1040 5% of patients who develop hypoglycemia with glucagon will have no hypoglycemia when glucagon is not given.
1041 If our expectation is correct, our planned sample size of 20 patients will provide ≥90% statistical power to detect
1042 a difference in hypoglycemia rates between the two arms. If this proportion is three times as big as we expect
1043 (15%), we will still have 82% power to detect the difference.

1044

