1045 **Statistical power of two-sided exact McNemar's test with 2.5% type 1 error, assuming a difference of 50% (25%**
1046 **vs. 75%) in hypoglycemia rate between two arms. Crossover design, N=20.**

Proportion discordant (higher value corresponds to lower correlation between two arms)	Proportion of those having hypoglycemia with glucagon	Statistical power
--	---	-------------------

	that do not have hypoglycemia when glucagon is withdrawn	
0.625†	25%	75%
0.6	20%	78%
0.575	15%	82%
0.55	10%	86%
0.525	5%	90%
0.505	1%	93%

1047 †corresponding to independence between two arms

1048

1049 **Power Calculation for Aim 2**

1050 No formal power analysis has been completed for the determination of a relationship between VOCs and
1051 hypoglycemia. Combining hypoglycemia that occurs during exercise and hypoglycemia that occurs after a
1052 correction bolus with a glucose target of 50 mg/dl, we expect to capture breath and sweat in at least 30 visits
1053 during which hypoglycemia (BG < 60 mg/dl) occurs. During visits in which hypoglycemia occurs, we will capture
1054 at least one set, and likely 2 or more sets, of samples of breath and sweat during hypoglycemia, and at least 4
1055 during normoglycemia in the same participants on the same day. This is anticipated to provide samples from 30-
1056 40 hypoglycemic episodes and paired samples during normoglycemia (both before and after hypoglycemia) from
1057 the same participants. If there is a robust correlation between a VOC marker and hypoglycemia, this should
1058 provide sufficient power to identify VOC markers of hypoglycemia.

1059

1060 **VII. Risks and Discomforts**

1061

1062 There is a risk of hypoglycemia. In the outpatient run-in period, this risk is expected to be less than the risk during
1063 the subjects' lives outside the trial based on data from earlier trials. All of our previous studies have shown that
1064 hypoglycemia is significantly reduced in all configurations of the bionic pancreas when compared with usual care.
1065 Based on our experience, we believe that the risk of hypoglycemia in the outpatient run-in period will be less
1066 than or equal to the risks that they are exposed to on a daily basis while living with type 1 diabetes outside of
1067 the trial. The exercise visit protocol is designed to cause hypoglycemia. Given frequent PG monitoring, protocols
1068 for treating hypoglycemia, and direct supervision by an RN or MD at all times, the risk of a hypoglycemic episode

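### The VOC analysis for Aim 2 does not separate hypoglycemia from glucagon exposure, so a compound that responds to glucagon could be mistaken for a hypoglycemia marker

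*Combined protocol and SAP*

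**What the plan says.** Section II: "Twenty subjects will participate in two experimental periods". In one of them, "glucagon will be replaced with a placebo during the exercise visit". Aim 2 collects breath and sweat at both exercise visits, more often during hypoglycemia, and leaves the analysis to the collaborating laboratory.

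Section VI.b.3 places the VOC outcomes under other endpoint analyses. The first reads "Identification of volatile and organic compound or compounds in breath and sweat that correlate(s" and goes on to name hypoglycemia. No model is given.

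Section VI.c (Aim 2) adds episodes during exercise to those after the syringe insulin: "correction bolus with a glucose target of 50 mg/dl, we expect to capture breath and sweat in at least 30 visits" with hypoglycemia. It anticipates 30 to "40 hypoglycemic episodes and paired samples during normoglycemia (both before and after hypoglycemia) from" the same participants. It states that there is no formal power analysis for this aim.

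Section I.b describes the controller: "Glucagon dosing is based on the glucose level and rate of descent". It adds that dosing may occur "preemptively even if glucose is above range and it includes a feedback term to account for the pending effects" of recent doses.

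**The concern.** In a glucagon visit, glucose state and glucagon exposure are linked by design, because the controller doses when glucose is low or falling. A hypoglycemic sample there is likely to be a glucagon-exposed sample as well. If the hypoglycemic-versus-normoglycemic contrast ignores arm and dose, an effect of glucagon on breath or sweat enters the estimated effect of hypoglycemia.

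Section I.a gives the purpose as a non-invasive warning device for people with diabetes, who in general do not wear a glucagon pump. A compound that tracks glucagon would not serve them. The trial already randomises each participant to a glucagon-free visit in which the two can be told apart, but no section says the VOC analysis will use it.

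**Working it through.** **Inputs from the protocol.** 20 completers with two visits each, so 20 glucagon and 20 placebo visits (sections II and IV.a). Hypoglycemia rates from section VI.c: "we expect the hypoglycemia rate to be around 25% in the bi-hormonal arm and around 75% in the insulin-only" arm. At least 30 hypoglycemic visits (section VI.c, Aim 2). Syringe insulin only where hypoglycemia has not already occurred (sections I.d and V.d.v).

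**Check of the 25% and 75% rates.** With s the share of those hypoglycemic on glucagon who are not hypoglycemic without it, the discordant proportion is 0.50 + 2 × 0.25 × s. Exact McNemar power by enumeration (N = 20, two-sided 0.025) for s = 25, 20, 15, 10, 5 and 1% is 75.0, 78.4, 81.9, 85.7, 89.8 and 93.3%. The plan's table gives 75, 78, 82, 86, 90 and 93%, so every row reproduces.

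**The Aim 2 count.** Before the injection, 20 × 0.25 = 5 glucagon visits and 20 × 0.75 = 15 placebo visits have hypoglycemia, 20 in all. The injection then goes to 15 glucagon and 5 placebo visits. With success rate q, equal in both arms:
- glucagon visits with hypoglycemia: 5 + 15q
- placebo visits with hypoglycemia: 15 + 5q
- total: 20 + 20q

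The plan does not state q, so its figure of 30 cannot be fully reproduced. It needs q ≥ 0.5.

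| q | Total | Glucagon | Placebo | Glucagon share |
|---|---|---|---|---|
| 0 | 20 | 5 | 15 | 25% |
| 0.5 | 30 | 12.5 | 17.5 | 42% |
| 1 | 40 | 20 | 20 | 50% |

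If success differs by arm, a total of 30 needs 15 × (glucagon success) + 5 × (placebo success) = 10. Placebo success of 1 gives glucagon success of 1/3 and a glucagon share of 10/30 = 33%. Placebo success of 0 gives 2/3 and 15/30 = 50%.

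**A bound free of event rates.** Placebo visits cannot exceed 20, so at least 30 − 20 = 10 hypoglycemic visits must be glucagon visits.

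**How a glucagon-only effect enters.** In a within-visit contrast that ignores arm and dose:

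shift = (glucagon share) × (exposure of hypoglycemic samples − exposure of normoglycemic samples) × (glucagon effect)

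**Illustration.** All of the following are assumptions: 12 glucagon and 18 placebo hypoglycemic visits; one hypoglycemic sample minus the mean of four normoglycemic samples; SD 1 per sample; one-sample t-test at 0.05; 4,000 runs. The simulated VOC responds to glucagon and not to hypoglycemia. For a 1 SD effect and exposure of 90% versus 10%, the shift is 12/30 × 0.8 × 1 = 0.32 SD. The standard error is √(1.25/30) = 0.20. Share of runs in which the VOC is flagged as a hypoglycemia marker:

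| Exposure, hypoglycemic vs normoglycemic | 0.5 SD | 1 SD | 2 SD |
|---|---|---|---|
| 90% vs 10% | 11% | 29% | 68% |
| 90% vs 50% | 6% | 11% | 24% |
| 90% vs 90% | 5% | 5% | 5% |

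In placebo visits alone the rate stays at about 5% throughout.

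**Between visits the direction reverses.** Before the injection, 5 of 20 hypoglycemic visits (25%) are glucagon visits, against 15 of 20 non-hypoglycemic visits (75%). An unpaired analysis across visits could bias the other way and hide a true marker.

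**Safeguards looked for.** Section VI.b.3 has no arm term or dose covariate for the VOC outcomes. The exploratory stratifiers under Analysis of Outpatient Outcomes include neither arm nor glucagon dose. Section VI.b.3 does list total glucagon dosing to the end of the visit, but does not link it to the VOC outcomes.

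**The case against.** The strongest reply is that the documents specify no VOC analysis, so there is no pooled test to criticise. Section VI.c gives an expected count of visits and does not mention arms. That is correct. Use of both visit types follows from the count; a pooled model does not. What stands is that nothing in the plan prevents such a model.

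A reader might also infer that glucagon effects would be reported as hypoglycemia markers. The documents do not support that. Nothing in them says that glucagon alters any VOC. Section V.b reports that mean glucagon levels in earlier inpatient studies exceeded the normal fasting range only 1% of the time and expects modest exposure. Those are averages from other settings and do not exclude peaks during exercise, but they weaken the premise.

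Nor do the documents show that normoglycemic samples are mostly free of glucagon. Dosing can be preemptive, and comparison samples are also taken after episodes. With equal exposure the bias vanishes.

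It would be too strong to say that the two effects cannot be separated within glucagon visits. About 15 of those 20 visits are expected to have no hypoglycemia before the injection and may supply exposed normoglycemic samples. The device stores dosing data, and section IX.a allows dosing records to go to the collaborator.

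Finally, restricting the main analysis to placebo visits would cut about 30 episodes to about 17.5 (at q = 0.5). Section I.c says that earlier work was limited by too few hypoglycemic participants. That objection stands, and the fix below keeps all samples.

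**Conclusion.** The point holds as a possible confounder that the plan leaves open. At least 10 of the 30 or more expected hypoglycemic visits are glucagon visits, given 20 completers. Glucagon dosing follows glucose in those visits, and neither arm nor dose is planned for in the VOC analysis.

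The size of the bias cannot be fixed from the documents. It depends on whether glucagon affects any VOC and on how often normoglycemic samples are exposed; neither is given. The simulated range, 5% to 68%, shows how much turns on these unknowns and is not a prediction. A reader might take the 42% share as the proportion of episodes under glucagon. It rests on an equal 50% injection success in both arms, and it counts visits, not exposed samples. The pre-injection split uses the primary-event rates, whereas Aim 2 needs only a glucose below 60 mg/dl, so 20 is a lower-end estimate.

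The endpoint is exploratory and Aim 1 is untouched. Severity is minor: a cheap improvement.

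**What to change.** State the VOC analysis before the samples are analysed:

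- Keep all samples in a within-participant comparison of hypoglycemia with normoglycemia. Include visit arm and time-stamped recent glucagon dose (zero in placebo visits) as covariates. The arm term handles differences between visits and the dose term those within visits.
- Call a compound a hypoglycemia marker only if it shows the same association in placebo-visit samples alone.
- Compare candidate compounds between glucagon and placebo visits at normoglycemia.
- Flag samples taken after the syringe insulin or after oral carbohydrate, since these also track glucose state.
- Send visit assignment and dose times with the de-identified data. The glucagon pump holds saline in placebo visits, and the device may log those doses as glucagon. Add dose timing to the exercise-visit data list in section VI.a.3, which does not name it.

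The cost is analysis wording and one more field in the data transfer; no visits or samples are added. The placebo confirmation set is smaller, at 15 to 20 hypoglycemic visits at the plan's rates (15 + 5q), so a weak true marker may fail confirmation.

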- 551 • Subjects will remain at all times within a geographic boundary established on the basis of 250 miles
552 from the designated base for study personnel and will avoid any air travel.
- 553 • Subjects will keep a charged mobile phone on their person (or at their bedside) at all times and will
554 answer calls from the study staff.
- 555 • Subjects will sleep in a hotel nearby the Diabetes Research Center the night prior to both exercise
556 visits. This is meant to avoid increases in counter-regulatory and stress hormones that may occur
557 during a lengthy and/or stressful commute to the study center.
- 558 • Study subjects will keep a StatStrip Xpress glucometer easily accessible at all times in case a
559 calibration is needed, and they will do all calibrations with this meter. They will keep a glucometer,
560 fast-acting carbohydrates, and a glucagon emergency kit easily accessible at home for hypoglycemia
561 as needed.
- 562 • Subjects should use the study provided StatStrip Xpress glucometer for all BG checks throughout the
563 study. They are encouraged to check their BG at least four times a day, before meals and before
564 bedtime. They will also be encouraged to check before exercise and at intervals during exercise, and
565 for any symptoms of hypoglycemia. There are no restrictions on additional checks and subjects
566 should check as often as they wish to confirm the accuracy of the Dexcom CGM and for safety.
- 567 • Subjects will wear 6 mm steel cannula (contact detach) infusion sets during both the outpatient run-
568 in periods and both exercise visits.
- 569 • Subjects will not use any recreational drugs or drugs of abuse, other than alcohol. The need to take
570 prescription drugs that dull the sensorium, reduce sensitivity to symptoms of hypoglycemia, or
571 hinder appropriate decision-making may be grounds for exclusion from the trial or discontinuation
572 of participation, a decision that will be made by the principal investigator.
- 573 • Subjects may not take acetaminophen during both study arms due to potential interference with

- 574 CGM sensing. Acetaminophen is known to interfere with the accuracy of the Dexcom CGM.
- 575
- 576
- 577
- 578
- 579
- 580
- 581
- 582
- 583
- 584
- 585
- 586
- 587
- 588
- 589
- 590
- 591
- 592
- 593
- 594
- 595
- 596
- 597
- 598
- 599
- 600
- 601
- 602

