- 663 ● The subject's own insulin infusion pump will be stopped and disconnected, and its infusion set will be
- 664 removed.
- 665 ● The staff will start the bionic pancreas as close as possible to a minute divisible by 5 minutes (i.e. on a 5-
- 666 minute mark). Study staff will verify that data streaming is working prior to the subject leaving the
- 667 Diabetes Research Center.

669 **Outpatient Run-In:**

- 670 ● The subjects will calibrate the Dexcom CGM twice daily, preferably before breakfast and supper, using
- 671 the StatStrip Xpress.

- 672
- 673
- 674
- 675
- 676
- 677
- 678
- 679
- 680
- 681
- 682
- 683
- 684
- 685
- 686
- 687
- 688
- 689
- 690
- 691
- 692
- 693
- 694
- 695
- 696
- 697
- 698
- 699
- 700
- 701
- 702
- 703
- 704
- 705
- 706
- 707
- 708
- 709
- 710
- 711
- 712
- 713
- 714
- 715
- 716
- 717
- 718
- 719
- 720
- 721
- Subjects will be advised to delay calibration if there is a steep rise or fall in the blood glucose (>2 mg/dl/min), or if they suspect a steep rise or fall while in blinded mode, there has been carbohydrate intake in the last 30 minutes, or there has been a glucagon dose in the last 15 minutes. In the immediate aftermath of carbohydrate intake or glucagon dosing it is possible for the BG to be rising without a change in interstitial fluid glucose. If a calibration is delayed for any of these reasons, it will be performed at the next opportunity.
 - Subjects may perform additional calibrations if the Dexcom CGM is inaccurate relative to a BG measurement as long as they do not calibrate within 30 minutes of food intake or 15 minutes of glucagon dosing. Subjects will be discouraged from performing extra calibrations if the Dexcom CGM is within 15 mg/dl when the BG is \leq 75 mg/dl and within 20% if the BG is >75 mg/dl at times when the rate of change is low. They will also be trained to understand that the apparent error can be higher than this when the BG is changing rapidly, and that it is typical for the Dexcom CGM to underestimate BG when the trend is upward and to overestimate BG when the trend is downward as a result of physiologic lag. Errors in these directions should typically not prompt extra calibrations unless they are very large (\geq 50%).

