1099 will be required by in order to approve a bionic pancreas delivering glucagon on a chronic basis.

1100

1101 The data derived from this study will allow us to evaluate whether or not there is a relationship between
1102 volatile organic compounds in the breath and sweat and hypoglycemia. This information could be useful in
1103 developing noninvasive technologies to identify impending and actual hypoglycemia.

1104

1105 Subjects will be financially compensated for participating in the study.

1106

1107 **IX. Data and Safety Monitoring**

1108 **IX. a. Monitoring of Source Data**

1109

1110 During the experiment, Dexcom CGM data will be collected in various ways. Dexcom CGM data, calibration data,
1111 insulin dosing data, and glucagon dosing data will be automatically stored in the bionic pancreas device (from
1112 which it will be downloaded at intervals) and wirelessly streamed to the cloud where it will be stored to provide
1113 redundancy in data storage and mitigate the risk of data loss. All of the data will be combined in a single database
1114 that will be compared against the primary data files for integrity. The computer database will be backed up at
1115 least monthly and the backup media stored in a secure location.

1116

1117 Study staff will be encouraged to raise any concerns they may have or problems they have identified at any time.
1118 The PI, in consultation with the co-investigators, will decide a course of corrective action, and resolution or
1119 progress will be assessed no later than the next meeting.

1120

1121 An audit of procedures, regulatory documentation, and a sample of subject files will be performed by a member
1122 of the Diabetes Research Center at least biannually. The audit will be conducted by a staff member who is not
1123 directly involved in the conduct of the study. This audit will include a review of regulatory documentation, such

1124 as IRB and FDA correspondence, and a review of subject files, including a review of consents, case report forms,
1125 and other data from study visits.

1126
1127 A numeric code will be substituted for the subjects personal identifying information in the study database, which
1128 will be password protected. The key linking the medical record number of the subject with the numeric code,
1129 along with case report forms, and all information that is personally identifiable, will be kept in a locked filing

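### Outpatient CGM MARD is scored against meter values that include the fingersticks used to calibrate the same sensor

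*Combined protocol and SAP*

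**What the plan says.** Section VI.b.3, among the CGM-based outcomes of the outpatient period, names the measure: "CGM MARD from Dexcom G5 CGM versus time-stamped BG values from meter downloads (any other" "BG values will not be considered"). The comparator is therefore the whole set of time-stamped meter downloads from the run-in.

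The calibration rules use the same meter:

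- Section V.d.iii has subjects keep the StatStrip meter at hand in case a "calibration is needed, and they will do all calibrations with this meter". It also asks them to use that meter for all their glucose checks.
- Section V.d.iii on frequency: "They are encouraged to check their BG at least four times a day, before meals and before" bedtime.
- Section V.d.v (Outpatient Run-In): "The subjects will calibrate the Dexcom CGM twice daily, preferably before breakfast and supper, using" the StatStrip.
- Section V.d.v on extra calibrations: "Subjects may perform additional calibrations if the Dexcom CGM is inaccurate relative to a BG" measurement, subject to waiting times after food and glucagon. No number is set as a limit.
- Section V.d.v on timing: "Subjects will be advised to delay calibration if there is a steep rise or fall in the blood glucose", and also soon after carbohydrate or glucagon.

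Section IX.a lists "Dexcom CGM data, calibration data" among the records that the device stores automatically. No section says whether calibration fingersticks stay in the MARD, or whether the paired CGM value comes from before or after the calibration.

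**The concern.** MARD is meant to say how far the sensor strays from blood glucose. A fingerstick that has just been used to adjust the sensor is not an independent check on the adjusted reading. Because the rule admits every time-stamped download, these points enter the accuracy set as the plan is written.

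The gap in the pairing rule makes this worse. Two analysts could follow the plan faithfully, one taking the CGM value before the fingerstick and the other the nearest value in time, and report different MARDs from the same data.

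The stake is modest but real. For the run-in, the plan reports only CGM-based outcomes (Section VI, Analysis of Outpatient Outcomes), and this MARD is the only listed measure of paired agreement between those readings and blood glucose.

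**Working it through.** The documents state no MARD, number of pairs or calibration share, so there is no planned figure to reproduce. The inputs are two scheduled calibrations a day (V.d.v), at least four encouraged checks a day (V.d.iii), a run-in of 24 to 96 hours (V.d.v, Exercise Visits), and 20 subjects with two periods each (Aim 1), which gives 20 × 2 = 40 run-ins.

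**1. Share of pairs that are calibration points.** Share = calibrations per day ÷ meter values per day. The scheduled calibrations fall preferably before breakfast and supper and the encouraged checks before meals and bedtime, so the calibrations naturally form two of the four checks.

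| Calibrations/day | Meter values/day | Share |
|---|---|---|
| 2 | 3 | 67% |
| 2 | 4 | 50% |
| 2 | 6 | 33% |
| 2 | 8 | 25% |
| 3 (one extra) | 4 | 75% |

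If the two calibrations were additional to four checks, the share would be 2/(4 + 2) = 33%.

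**2. Direction of the effect.**

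- Downward: a pair matched to a CGM value already adjusted by that fingerstick understates the error. Delaying calibration during rapid change also steers calibration pairs toward stable glucose, where the error is likely to be smaller.
- Upward: extra calibrations are prompted by disagreement. V.d.v discourages them when the CGM is within 15 mg/dl at BG ≤75 mg/dl, or within 20% above that, at times when glucose is changing slowly. Paired with the preceding CGM value, these points are selected for large error.

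The documents do not settle which effect dominates.

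**3. Size, as an illustration only.** Let M be the MARD on non-calibration pairs, s the calibration share, and r the error of calibration pairs relative to M. Then reported MARD = s·r·M + (1 − s)·M. M = 10% is an assumption, and the documents give no value for M or r.

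| s | r = 0 | r = 0.5 | r = 1 |
|---|---|---|---|
| 1/3 | 6.7% | 8.3% | 10% |
| 1/2 | 5.0% | 7.5% | 10% |
| 2/3 | 3.3% | 6.7% | 10% |

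For s = 1/2 and r = 0.5: 0.5 × 0.5 × 10 + 0.5 × 10 = 7.5. Any r above 1 gives a reported MARD above 10%.

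**4. Pairs left after exclusion, at four checks a day.**

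- 24-hour run-ins: 40 × 4 × 1 = 160 pairs, less 40 × 2 × 1 = 80 calibrations, leaves 80.
- 96-hour run-ins: 40 × 4 × 4 = 640 pairs, less 40 × 2 × 4 = 320 calibrations, leaves 320.

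**5. Pairs available in clinic, for the optional addition.** Take 60 minutes of exercise and 30 minutes of follow-up, with the sampling intervals of V.d.v.

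- PG ≥80 mg/dl in exercise and ≥120 mg/dl afterwards: (60/10 + 1) + 1 = 8.
- PG ≥80 mg/dl in exercise and 80–119 mg/dl afterwards: (60/10 + 1) + 30/10 = 10.
- PG <80 mg/dl throughout: (60/5 + 1) + 30/5 = 19.

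Over 40 visits this is 320 to 760 pairs. Visits that reach the hypoglycemia threshold have a different length and are not modelled.

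**The case against.** The strongest reply is that little depends on this figure. MARD is one of many descriptive outcomes under the other endpoints. Both run-ins are bi-hormonal, so it supports no treatment comparison, and the primary endpoint rests on YSI plasma glucose. A fingerstick is also taken before it is entered as a calibration, so an analyst who pairs it with the preceding CGM value avoids the circularity. All of this stands and sets the weight of the point. It does not remove the point, because the plan does not state that pairing and its comparator set includes the calibration values.

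A reader might also infer four stronger things that the documents do not support:

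- **That the restriction discards YSI pairs.** It governs an outpatient outcome, and V.c places the YSI at the exercise visit only. There are no outpatient YSI values to exclude.
- **That half is the most the calibration share can be.** Four checks are encouraged, not required, and extra calibrations have no numerical cap. The share can lie on either side of 50%.
- **That the reported MARD would be half the true one.** That is the r = 0 extreme at a 50% share. It requires every calibration pair to use an already adjusted CGM value with no residual error.
- **That the plan cannot show accuracy where the controller needs it.** The controller doses from CGM throughout the run-in, which is the period this MARD covers. Fingersticks at low alarms and for symptoms will yield some low-range pairs. In clinic, mean glucose, time in range and time in hypoglycemia are reported from both plasma glucose and CGM. Such summaries are not point-by-point accuracy, but the plan is not silent.

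**Conclusion.** The point holds as a minor fault in a stated analysis rule. As written, the outpatient MARD mixes independent checks with calibration points, at about 50% of pairs under the encouraged schedule if the two calibrations are among the four checks. The reported figure could be too low or too high. The 5.0% to 10% range is an illustration that rests on an assumed MARD of 10%, a 50% share and r between 0 and 1; it is not a forecast.

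The consequence is confined to how far a reader can trust this one accuracy figure, and the CGM-based run-in outcomes that it supports. The primary analysis and its power are untouched. The absence of a paired CGM-versus-YSI measure in clinic is not an error, since CGM accuracy is in neither aim.

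**What to change.** In VI.b.3, compute the main outpatient MARD on time-stamped meter values not used for calibration, identified from the calibration data stored under IX.a. Pair each with the last CGM value recorded before the fingerstick, and state the longest gap allowed. Keep the restriction to time-stamped downloads. Report the MARD on all values as a sensitivity figure, with the number of calibration and non-calibration pairs.

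The cost is a change of analysis wording, a match of meter downloads to the calibration log, and fewer pairs: about 80 to 320 instead of 160 to 640 at four checks a day. No new data are needed.

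Optional and separate: 5-minute CGM and YSI readings are both available in clinic, so a paired CGM-versus-YSI MARD could be added under the exercise-visit endpoints, overall and for PG <70 and ≥70 mg/dl. It would draw on about 8 to 19 pairs per visit under the assumptions in the working.
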